#### 10.3.2 Related to clotrimazole

Side-effects associated with clotrimazole troches are rare and may include nausea, vomiting, unpleasant mouth sensations, and pruritus.

#### 10.3.3 Related to blood collection

Minor complications including bleeding, pain, and hematoma formation at the site of blood draws or infections may rarely occur.

#### 10.3.4 Related to tissue biopsy

Oral mucosal punch biopsy is a minor surgical procedure that may be associated with temporary bleeding, hematoma at the site, local infection and postoperative discomfort. These risks are small (generally <5%) and transient.

### 10.3.5 Related to pregnancy and nursing mothers

Although dexamethasone will be applied topically to the oral cavity in this study, some amount of medication may be absorbed into the bloodstream. Strong corticosteroids have caused birth defects in animals. It is not known whether topical steroids are absorbed in sufficient amounts to appear in breast milk. Therefore, pregnant and nursing women will not be eligible to participate in this study. Women of childbearing potential will be required to use an effective method of contraception.

### 10.3.6 Related to saliva collection

Subjects who have undergone transplant may have decreased salivary function and find it difficult to produce a saliva sample. A mild citric acid solution will be placed on the tongue to elicit salivation, and the saliva will be collected using mild suction. Subjects might experience a sour taste and mild discomfort from the citric acid and oral suctioning.

### 10.3.7 Related to quality of life assessments

There are little to no risks involved in completing the quality of life assessment measures.

## 10.4 Risks in Relation to Benefits

### 10.4.1 For adult subjects

The risks of participating in this trial are limited to side effects of dexamethasone and clotrimazole, the risks of standard diagnostic procedures (oral mucosal biopsy), the collection of saliva, the completion of quality of life assessments and an additional blood sample to be used strictly for research purposes. Samples for clinical monitoring will be collected during sample collection procedures that are part of their routine post transplant care.

The benefits to the subjects could be prevention of oral chronic GVHD resulting in improved quality of life, decreased morbidity associated with oral chronic GVHD (should it develop), and potentially, treatment with other more toxic therapies could also be avoided or postponed. Subjects will also receive direct health benefits due to thorough post transplant oral examinations, early diagnosis of oral chronic GVHD, and therefore earlier access to oral chronic GVHD management.

### 10.4.2 For pediatric subjects

The inclusion of children satisfies the criteria set forth in 45 Code of Federal Regulations 46, Subpart D: as follows:

(a) *“The risk represents a minor increase over minimal risk”*. The risks of participating in this trial are limited to side effects of dexamethasone and the collection of saliva. Samples for clinical monitoring will be collected during sample collection procedures that are part of their routine post transplant care. Only those laboratory tests approved by the IRB and involving not greater than minimal risk will be conducted. Research will not include genetic testing. Therefore, there is no genetic testing associated risk.

(b) *“The relation of the anticipated benefit to the risk is at least as favorable to the subjects as that presented by available alternative approaches”*. Post transplant subjects who co-enroll in this protocol are familiar with blood collection and hospital procedures due to their frequent need for monitoring for their primary disease and for post transplant care. The monitoring that will be done is with the monitoring for the primary transplant protocol. It only minimally exceeds what would be done post transplant (increased oral surveillance and saliva samples)

(c) *Adequate provisions are made for soliciting the assent of the children and permission of their parents or guardians, as set forth in 46.408. An assent form is available.*

## 10.5 Informed Consent

The investigational nature and research objectives of this trial, the procedure and its attendant risks and discomforts will be carefully explained to the subject. The potential subject will be educated regarding the nature of the condition, proposed intervention, and outcome measures. Study subjects will be informed that participation is entirely voluntary and that withdrawal from the study can be made at any time without penalty of benefits to which they may be entitled.

At any time during participation in the protocol that new information becomes available relating to risks, adverse events, or toxicities, this information will be provided orally or in writing to all enrolled or prospective subject participants. Documentation will be provided to the IRB and if necessary the informed consent amended to reflect relevant information.

We anticipate the enrollment of non-English speaking research participants into our study. The IRB approved full consent document will be translated into that language in accordance with the Clinical MAS Policy M77-2. If there is an unexpected enrollment of a research participant for which there is no translated extant IRB approved consent document, the principal investigator and or those authorized to obtain informed consent will use a short form oral consent process as described in MAS Policy M77-2, 45CFR 46.117(b)(2), 21CFR50.27. The summary that will be used is the English version of the extant IRB approved consent document.

We request prospective IRB approval of the use of the short form for up to 3 participants in a given language and will notify the IRB at the time of continuing review of the frequency of the use of the short form. Should we reach a threshold of 3, we will notify the IRB of the need for an additional usage of the short form and that we will have that consent document translated into the given inherent language.

## 10.6 Compensation

Compensation will be provided for those subjects participating in the study based on the below values consistent with NIH and NHLBI guidelines. Subject who are ineligible or choose not to have the procedure will receive only partial payment.

### Per Subject Enrolled

Procedure(s)/Test(s)	IU*	\$	Frequency	Total \$
Blood Draw	1	10	3	\$30
Serial Blood Draw	1	10	1	\$10
Research Blood Draw	1	10	3	\$30
Patient Questionnaire #1	1	10	3	\$30
Patient Questionnaire #2	1	10	3	\$30
Patient Questionnaire #3	1	10	3	\$30
Patient Questionnaire (for adults) #4	1	10	3	\$30
Oral Exam	2.5	25	3	\$75
Buccal Mucosal Bx (research)	5	50	3	\$150
Research Salvia Sample	1	10	3	\$30
Drug Administration, General	2	20	2	\$40
Telephone Follow Up	1	10	7	\$70
OUTPATIENT- 1st HOUR	NA	20	3	\$60
OUTPATIENT TIME- Not to Exceed More than 4 Hours	1	10	6	\$60

ESCORT FEE- INPATIENT				
OUT PATIENT				
TOTAL \$				\$675

## 10.7 Travel Reimbursement

Reimbursement for local travel, US travel, food and lodging will be in accordance with NHLBI travel policy reimbursement and will be consistent with NIH and NHLBI guidelines.

## 10.8 Conflict of Interest

The Principal Investigator assured that each associate investigator listed on the protocol title page received a copy of the NIH's guide to preventing conflict of interest. Investigators added subsequent to the initial circulation were provided a copy of the document when they were added. Copies of the Conflict of Interest Statement were forwarded to the Clinical Director. No initial or subsequent members of the research team have reported a potential conflict of interest.

# 11. PHARMACEUTICALS

## 11.1 Dexamethasone Oral Solution

*Other:* Dexamethasone sodium phosphate, Decadron.

*Classification:* Corticosteroid. 07-H

*Action:* Anti-inflammatory and immunosuppressive. Dexamethasone is a corticosteroid with mainly glucocorticoid activity; 750 micrograms of dexamethasone is equivalent in anti-inflammatory activity to about 5 mg of prednisone.

*Supply / availability:* Commercially available dexamethasone 0.01% (0.5mg/5 mL) solution will be repackaged, labeled, and dispensed by NIH Clinical Center Pharmacy under USP <795> guidelines and FDA 503a regulations.

*Product description:* Dexamethasone oral solution 0.01% (100mcg/mL or 0.5 mg/5 mL) is a clear, colorless solution available commercially in a 500 mL bottle.

*Active ingredient:* dexamethasone sodium phosphate.

*Inert ingredients:* Flavoring, glycerin, propylene glycol, methylparaben, propylparaben, sorbitol water.

*Preparation:* The commercially available solution will be repackaged in 8 ounce amber bottle and relabeled as study drug for the purposes of this study and to allow blinding of the subject, clinical staff, and investigators.

*Storage:* Store at room temperature (20o to 25oC , 68o to 77oF, controlled room temperature).

*Administration:* Rinse oral cavity for 2 minutes and spit out. Use 3 times daily after meals. DO NOT SWALLOW. Do not eat or drink for 30 minutes after use.

*Dose:* 10 mL (1mg).

*Toxicities:* see section 10.3.1.

## 11.2 Study Placebo Oral Solution

*Supply:* The placebo solution will be repackaged, labeled, and dispensed by NIH Clinical Center Pharmacy under USP <795> guidelines and FDA 503a regulations for the purpose of this study and to allow blinding to subject, clinical staff, and investigators.

*Product description:* The placebo oral solution contains the following ingredients: glycerin, propylene glycol, methylparaben, propylparaben, sorbitol, cherry flavoring, and water for injection.

*Storage:* Store at room temperature (20° to 25°C , 68° to 77°F controlled room temperature).

*Administration:* Rinse oral cavity for 2 minutes and spit out. Use 3 times daily after meals. DO NOT SWALLOW. Do not eat or drink for 30 minutes after use.

*Dose:* 10 mL.

### 11.3 Clotrimazole Oral Troches

*Other:* Clotrimazole oral lozenge; Mycelex®(Bayer).

*Classification:* Antifungal.

*Action:* Antifungal.

*Supply / availability:* Commercially available; various manufacturers.

*Product description:* Clotrimazole oral troches 10mg.

*Active ingredient:*

Clotrimazole ([1-(o-chloro- $\alpha$ , $\alpha$ -diphenylbenzyl) imidazole].

*Inert ingredients:*

Dextrose

Cellulose, Microcrystalline

Modified Cellulose Gum

Povidone

Magnesium Stearate.

*Storage:* Store at room temperature (20° to 25°C , 68° to 77°F controlled room temperature).

*Administration:* Dissolve in the oral cavity twice daily. Do not eat or drink for 30 minutes after use.

*Dose:* 10 mg.

*Toxicities:* see section 10.3.2.

## **APPENDIX A : SCALE FOR ORAL PAIN**

### **Scale for Oral Pain**

On a 0 to 10 scale, how SENSITIVE OR PAINFUL was your mouth at its WORST in the past month? Please circle.

**0      1      2      3      4      5      6      7      8      9      10**

### **Scale for Xerostomia**

On a 0 to 10 scale, how DRY was your mouth at its WORST in the past month? Please circle.

**0      1      2      3      4      5      6      7      8      9      10**

### **Patient-assessed Global Scale**

Compared to one month ago, the overall condition of your mouth today is (please circle)

Much worse              A little worse              Same              A little better              Much better

## APPENDIX B : GVHD SEVERITY SCALE

### GVHD Severity Scale (adapted from Piboonniyom S et al, 2005)

The severity of the lesions in each site was scored according to the presence of reticular/hyperkeratotic, erosive/erythematous, and/or ulcerative lesion(s) as follows: reticular/hyperkeratotic lesions were scored from 0 to 1 (0 = no white striations, 1 = presence of white striations or keratotic papules); erosive/erythematous areas were scored from 0 to 3 by area of involvement (0 = no lesion, 1 = lesions less than 1 cm^2, 2 = lesions from 1 to 3 cm^2, 3 = lesions greater than 3 cm^2); ulcerative areas were scored from 0 to 3 by area of involvement (0 = no lesion, 1 = lesions less than 1 cm^2, 2 = lesions from 1 to 3 cm^2, 3 = lesions greater than 3 cm^2).

Site	Reticular area		Erythematous area			Ulcerative area				
	0	1	0	1	2	3	0	1	2	3
Upper/lower labial mucosa	0	1	0	1	2	3	0	1	2	3
Right buccal mucosa	0	1	0	1	2	3	0	1	2	3
Left buccal mucosa	0	1	0	1	2	3	0	1	2	3
Dorsal tongue	0	1	0	1	2	3	0	1	2	3
Ventral tongue	0	1	0	1	2	3	0	1	2	3
Floor of mouth	0	1	0	1	2	3	0	1	2	3
Hard palate mucosa	0	1	0	1	2	3	0	1	2	3
Soft palate/tonsillar pillars	0	1	0	1	2	3	0	1	2	3
Maxillary gingiva	0	1	0	1	2	3	0	1	2	3
Mandibular gingiva	0	1	0	1	2	3	0	1	2	3
Total										

For each of the 3 clinical signs, a score was derived by summation of the scores of all 10 areas: reticular score =  $\Sigma R$ , erythema score =  $\Sigma E$ , and ulcerative score =  $\Sigma U$  (REU score) with a total weighted score of  $\Sigma R + \Sigma(E \times 1.5) + \Sigma(U \times 2.0)$ .

## APPENDIX C : ORAL GVHD SEVERITY SCALE

**Lichen Planus (Oral GVHD) Severity Scale** (adapted from Thongprasom K et al, 2003)

Score 5:	White striae with erosive area > 1 cm 
Score 4:	White striae with erosive area < 1 cm 
Score 3:	White striae with erythematous area > 1cm 
Score 2:	White striae with erythematous area < 1 cm 
Score 1:	Mild white striae only
Score 0:	No lesions, normal mucosa

## APPENDIX D : OHIP-14

### Oral Health Impact Profile (OHIP-14)

	Subject Name					
	Medical Record Number					
	Date					
#	Because of problems with your teeth, denture or mouth have you...	Never (0)	Hardly ever (1)	Occasionally (2)	Often (3)	Very Often (4)
1	Had trouble pronouncing words					
2	Felt sense of taste has worsened					
3	Had painful aching in the mouth					
4	Found it uncomfortable to eat any foods					
5	Have been self-conscious					
6	Felt tense					
7	Had an unsatisfactory diet					
8	Had to interrupt meals					
9	Found it difficult to relax					
10	Have been a bit embarrassed					
11	Have been irritable with other people					
12	Had difficulty doing usual jobs					
13	Felt life in general was less satisfying					
14	Have been totally unable to function					
	Total					

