## PRÉCIS

Prevention of oral chronic graft versus host disease (GVHD) by topical agents is an attractive strategy because it would potentially avoid the adverse effects associated with systemic immunosuppression. Topically administered dexamethasone solution is a commonly used agent for the prophylaxis of oral inflammatory conditions including GVHD. However, the efficacy and systemic effects of topically administered dexamethasone solution are unknown. We therefore propose this trial designed to evaluate the efficacy and safety of topical dexamethasone solution for prevention of oral chronic GVHD in stem cell transplant recipients.

This pilot phase II study will follow a randomized, double-blind, placebo controlled, parallel group design. Consenting subjects who have undergone hematopoietic stem cell transplantation at the NIH Clinical Center and the surrounding transplant clinics will be randomized 50/50 to receive dexamethasone 0.01% solution or placebo as an oral rinse for 3 months starting 90-100 days post-transplant. Subjects will be evaluated monthly after the start of intervention. Diagnostic and research evaluations will include a complete oral examination, oral mucosal biopsy prior to the beginning of the intervention (day -7) and at the time of development of oral chronic GVHD or at the completion of intervention in the absence of clinical GVHD. We will measure serum dexamethasone levels and perform short cosyntropin (ACTH stimulation) test at the end of the 3 months of intervention or onset of clinically significant GVHD.

The primary objective of the study is to evaluate the safety and efficacy of topical dexamethasone 0.01% solution used as an oral rinse for prevention of oral chronic GVHD. Our primary endpoint will be the proportion of subjects that develop clinically significant (severity score 3 or higher) oral chronic GVHD after three months.

Secondary objectives will include the impact of oral chronic GVHD on the quality of life, characterization of the changes in tissue and salivary biomarkers associated with development of oral graft versus host disease, and measures of the effects of topical dexamethasone on hypothalamo-pituitary-adrenal axis. Secondary outcomes will include oral cavity specific quality of life as measured by OHIP-14 questionnaire, oral discomfort levels, improvement in general quality of life scores, and severity of oral chronic GVHD as measured by the site-specific GVHD scoring system.

---

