#### **6.1.2 Baseline assessments**

- Serum chemistry (Acute Care (Na, K, Cl, CO2, Creatinine, Glucose, and Urea Nitrogen), Mineral (Phosphorus, Magnesium, Albumin, and Calcium), Hepatic (Alk Phosphatase, ALT, AST, Total Bilirubin, and Direct Bilirubin), and Other (Total Protein, CK, Uric Acid, and LD) panel) done concurrently with post transplant monitoring
- Pregnancy test (females of child bearing potential)
- Serum cortisol level (results blinded to investigators)
- The 0-10 Scale for Oral Pain (see Appendix A)
- The 0-10 Scale for Oral Xerostomia (see Appendix A)
- GVHD Severity Scale (see Appendix B)
- Lichen Planus (Oral GVHD) Severity Scale (see Appendix C)
- Disease specific quality of life - OHIP-14 scale (ages 18 and older only-Appendix D)
- Oral photographs (Optional)
- Oral lesion documentation
- Buccal mucosal less than approximately 6mm punch biopsy (ages 18 and older only) (optional)
- Research blood sample collection
- Research saliva sample collection
- Growth chart (length for age, weight for age percentiles and body mass index for age percentiles, pre-pubertal children) (if a hand x-ray is available on parent transplant protocol, the results will be reviewed)

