#### **8.4.4 Oral Health Impact Profile-14**

Oral Health Impact Profile-14 (OHIP-14, Appendix D) is a 14 item questionnaire developed to assess the state of oral health as perceived by a patient [50, 51]. Increased use of patient centered outcome measures has been advocated in the recent years. Patient centered outcome measures complement objective measures

to provide a more complete picture of the impact of disease and treatment. OHIP-14 has been used in oral disease studies including oral lichen planus (a dermatological condition with manifestation similar to chronic oral GVHD). It has been shown to have high validity and reliability, and to be sensitive to treatment effects. This scale has not been well studied in children; therefore it will be limited to adults.

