### 8.5 Data Analyses

This study will be analyzed according to the “intent to treat” principle, that is, all randomized subjects will be included. Subjects not evaluated for endpoints will be considered to have reached the primary endpoint. Every effort will be made to reach and evaluate the subjects at the monthly intervals and at the end of the 3 month intervention period. The differences in proportions of significant oral chronic GVHD will be assessed by a chi-squared test (with continuity correction). Treatment group differences in the severity scores, pain and xerostomia scores, and quality of life scores (OHIP-14) will be assessed using the Wilcoxon test. Adjustments will be made for age and other covariates of interest, such as systemic immunosuppression. Adverse events will be tabulated by severity and treatment assignment. For pediatric subjects, analyses will include growth assessment (growth chart [length for age, weight for age percentiles

and body mass index] for age percentiles) and bone age and the associated z-scores (the number of standard deviations the child's measures [weight, height etc] differ from the population mean).

The intervention period will be 3 months. Should the subject reach the primary endpoint (development of clinically significant oral chronic GVHD), the subject will be asked to participate in end of study assessments and then will go off study. Subjects who did not develop oral chronic GVHD in the intervention phase of the study will be followed for up to 6 months to document late development of oral chronic GVHD. All subjects will be evaluated after 6 months after completion of the intervention phase of the study in the absence of clinical oral GVHD. Final statistical analysis will be performed once all subjects in the sample have completed the study and all records have been collected. We will use stratified analyses to account for effects of systemic immunosuppressive agents and other prognostic factors.

In the event of a protocol violation, the aggregate data will be analyzed with and without those subjects involved in the incident.

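### The OHIP-14 form states no recall period, so month-3 answers can include pre-rinse time and the secondary quality-of-life comparison can be attenuated and noisier

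*Combined protocol and SAP*

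**What the plan says.** Section 8.4.4 says that OHIP-14 "is a 14 item questionnaire developed to assess the state of oral health as perceived by a patient" and gives no recall period. The printed form in Appendix D opens "Because of problems with your teeth, denture or mouth have you", followed by 14 items rated from Never (0) to Very Often (4). The stem, the response headings and the items carry no time window.

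The other patient-reported scales, in Appendix A, are anchored. Pain asks "how SENSITIVE OR PAINFUL was your mouth at its WORST in the past month", xerostomia asks "how DRY was your mouth at its WORST in the past month", and the global scale begins "Compared to one month ago, the overall condition of your mouth today is".

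The baseline list in section 6.1.2 includes "Disease specific quality of life - OHIP-14 scale (ages 18 and older only-Appendix D", and the form is repeated at month 3 (6.3) and end of study (6.5). None of these lists adds a window. Section 8.5 says that "quality of life scores (OHIP-14) will be assessed using the Wilcoxon test". It allows adjustment for age and other covariates of interest but does not name baseline OHIP-14. The Précis sets the rinse "for 3 months starting 90-100 days post-transplant".

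**The concern.** A frequency rating has no fixed meaning without a period to which it refers. One subject may answer for the last few weeks, another for all the time since transplant. By month 3 a long window takes in weeks before the first dose, when neither arm had been treated. That shared experience pulls the two arms' scores together, and the mixture of windows adds variation between subjects.

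At stake is the oral-health quality-of-life part of the secondary hypothesis in 8.1.2 and objective 1.2.2. OHIP-14 is the only quality-of-life questionnaire in the visit lists, and section 2.2 says that the impact of oral chronic GVHD on quality of life after transplantation has not been studied. An analyst cannot repair the gap afterwards, because subjects answer the form as printed.

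**Working it through.** **The plan's own figure.** Section 8.2 powers only the primary endpoint: 15% versus 45%, significance level 0.05 (two-sided assumed), 80% power, 36 per arm. With pooled variance and no continuity correction:

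n = [1.96·√(2·0.30·0.70) + 0.842·√(0.15·0.85 + 0.45·0.55)]² / 0.30² = (1.270 + 0.515)² / 0.09 ≈ 35.4, so 36 per arm. Power at 36 is 80.7%. The figure reproduces, and the recall period does not affect it. For OHIP-14 the documents give no SD, expected difference or power.

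**Share of on-rinse time at month 3.** Inputs are the start day (90-100 after transplant) and the rinse length (3 months, about 90 days), both from the Précis.

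- Start at day 90: month 3 is day 180, and 90/180 = 0.50.
- Start at day 100: month 3 is day 190, and 90/190 = 0.47.

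I use f = 0.48 on rinse and 0.52 before it. This applies only to a subject who recalls back to transplant.

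**Effect of averaging.** This model is an assumption, not something the documents state. Let the month-3 answer be 0.52·P + 0.48·O, where P is the pre-rinse experience and O the on-rinse experience, with equal variance and correlation r. The arm difference is multiplied by 0.48. The variance is multiplied by 0.52² + 0.48² + 2·0.52·0.48·r. Without baseline adjustment, the sample multiplier for the same power is

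m = (0.2704 + 0.2304 + 0.4992·r) / 0.2304.

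For an effect that would have 80% power with an on-rinse window, the remaining power (normal approximation standing in for the Wilcoxon test) is Φ(2.80/√m − 1.96).

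| r | m | Remaining power |
|---|---|---|
| 0 | 0.5008/0.2304 = 2.2 | 48% |
| 0.5 | 0.7504/0.2304 = 3.3 | 34% |
| 1 | 1.0000/0.2304 = 4.3 | 27% |

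With f = 0.50 the multiplier is 2 + 2r, so 2.0 to 4.0. If subjects answer about recent weeks, f = 1, m = 1 and nothing is lost.

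**Effect of baseline adjustment.** Suppose the baseline answer also runs back to transplant and measures P without error. After adjusting for it, the arm difference and the residual SD are both scaled by 0.48, so the standardised effect is not reduced by the averaging. Response error at baseline would leave part of the loss.

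**Direction.** Randomisation makes pre-rinse experience similar in the two arms, so carrying it into the month-3 answer moves the difference toward zero and does not favour one arm.

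**The case against.** The strongest reply is that nothing shows how subjects read the question. They may well answer about recent weeks, and then there is no loss. That stands: the documents support saying that the comparison can be attenuated, not that it is.

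A reader might infer that the effect is halved and that about four times the sample is needed. The documents do not support this. It takes whole-period recall as fact, and it shrinks the effect while leaving the SD unchanged, which in the averaging model corresponds to r = 1. Four-fold is near the top of the range. Baseline OHIP-14 is collected and 8.5 leaves room for further covariates, so part of the loss may be recoverable; but the plan does not name baseline OHIP-14, so this cannot be assumed.

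Timing also varies. Subjects who reach the endpoint have end-of-study assessments then and leave (5.3, 6.5, 8.5). One assessed in the first month would still report some pre-rinse weeks under a one-month window. At the scheduled end-of-study visit, a one-month window covers no rinse time. A stated window therefore makes the answers interpretable, but not every answer becomes an on-rinse answer.

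Finally, the text is Amendment AA, dated 2021, and section 8.2 already cites an observed event proportion at Amendment R in 2016. Some subjects have evidently been assessed, probably on the form as printed, and a change now would create two versions. That stands and shapes the fix. Section 8.4.4 describes the instrument as valid and reliable, but whether its source carries a recall window cannot be checked here.

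**Conclusion.** The point holds as a minor one. The omission is plain on the face of the form, no other section supplies a window, and the protocol's other patient-reported scales do better. The consequence is possible attenuation and extra noise in one secondary, adults-only outcome. The primary endpoint and its sample size are untouched.

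A reader might also infer a bias against the active rinse or in its favour. The design does not support that, because pre-rinse experience is comparable across arms by randomisation. The risk is that a real quality-of-life benefit is missed or understated.

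The size cannot be computed from the documents. The range runs from no loss (recall of recent weeks) to a 2.2- to 4.3-fold sample requirement (recall back to transplant, equal pre-rinse and on-rinse variance, correlation 0 to 1, no baseline adjustment).

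**What to change.** 1. Add 'In the past month' to the Appendix D stem, matching Appendix A, for subjects who have not yet completed the baseline form. Keep the same wording at all of a subject's visits. At month 3 (±7 days) this window contains no pre-rinse time.
2. Record the form version for each subject, and stratify or adjust the OHIP-14 comparison for it.
3. Name baseline OHIP-14 as a covariate in section 8.5. A plain Wilcoxon test takes no covariate, so state the adjusted method as well, for example a rank analysis of covariance. This also helps for subjects who answered the form without a window.
4. If collection is already complete, leave the form alone, use the baseline adjustment, and report the missing window as a limitation.

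The cost is one phrase on one form, a version field and a sentence or two in 8.5. The downside is two form versions in the dataset, with only approximate balance between arms within each version.
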